3.1. Confirming Progression

Unlike RECIST 1.1, iRECIST requires the confirmation of progression and uses the terms iUPD (unconfirmed progression) and iCPD (confirmed progression). Confirmatory scans should be performed at least 4 weeks, but no longer than 8 weeks after iUPD.

iCPD is confirmed if further increase in tumour burden, compared to the last assessment, is seen as evidenced by one or more of the following:

- Continued increase in tumour burden (from iUPD) where RECIST 1.1 definitions of progression had been met (from nadir) in target, non-target disease or new lesions
 - Progression in target disease worsens with an increase of at least 5 mm in the absolute value of the sum
 - Continued unequivocal progression in non-target disease with an increase in tumour burden
 - Increase in size of previously identified new lesion (s) (an increase of at least 5 mm in the absolute value of the sum of those considered to be target new lesions) or additional new lesions.
- RECIST 1.1 criteria are met in lesions types (target or non-target or new lesions) where progression was not previously identified, including the appearance of additional new lesions.

If iUPD is not confirmed at the next assessment, then the appropriate response will be assigned (iUPD if the criteria are still met, but no worsening, or iSD, iPR or iCR if those criteria are met compared to baseline). As can be seen in table 2, the prior documentation of iUPD does not preclude assigning iCR, iPR, or iSD in subsequent time-point assessments or as best overall response (BOR) providing that iCPD is not documented at the next assessment after iUPD.

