8.3.6 Analysis of Exploratory Endpoints

8.3.6.1 Comparison of RECIST 1.1 and iRECIST criteria

Given that pembrolizumab is an immunotherapy agent, disease progression will be defined by RECIST and iRECIST criteria (Appendix 5). Comparison of the proportion progression-free at 6 months using iRECIST will be performed using the same method as for the primary endpoint of RECIST 1.1. Additionally, McNemar's Test will be used to estimate the concordance between the two outcome measures.

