3.2. New lesions

New lesions should be assessed and measured as they appear using RECIST 1.1 criteria (maximum of 5 lesions, no more than 2 per site, at least 10 mm in long axis (or 15 mm in short axis for nodal lesions), and recorded as New Lesions-Target (NLT) and New Lesion-Non-Target (NLNT) to allow clear differentiation from baseline target and non-target lesions.

New lesions may either meet the criteria of NLT or NLNT to drive iUPD (or iCPD). However, the measurements of target lesions should NOT be included in the sum of measures of original target lesions identified at baseline. Rather, these measurements will be collected on a separate table in the case record form.

PD is confirmed in the New Lesion category if the next imaging assessment, conducted at least 4 weeks (but not more than 8 weeks) after iUPD confirms further progression from iUPD with either an increase of at least 5 mm in the absolute value of the sum of NLT OR an increase (but not necessarily unequivocal increase) in the size of NLNT lesions OR the appearance of additional new lesions.

Table S2: Time-point (TP) iResponse

| Target Lesions* | Non-Target Lesions* | New Lesions* | Time Point Response | |
|--|--|--------------|---------------------|---|
| | | | No prior iUPD** | Prior iUPD**; *** |
| iCR | iCR | No | iCR | iCR |
| iCR | Non-iCR/Non-iUPD | No | iPR | iPR |
| iPR | Non-iCR/Non-iUPD | No | iPR | iPR |
| iSD | Non-iCR/Non-iUPD | No | iSD | iSD |
| iUPD with no change OR decrease from last TP | iUPD with no change OR decrease from last TP | Yes | NA | NLs confirms iCPD if NLs were previously identified and increase in size (≥ 5 mm in SOM for NLT or any increase for NLNT) or number. If no change in NLs (size or number) from last TP, remains iUPD |
| iSD | iUPD | No | iUPD | Remains iUPD unless iCPD confirmed based in further increase in size of NT disease (need not meet RECIST 1.1 criteria for unequivocal PD) |
| iUPD | Non-iCR/Non-iUPD | No | iUPD | Remains iUPD unless iCPD confirmed based on: o further increase in SOM of at least 5 mm, otherwise remains iUPD |
| iUPD | iUPD | No | iUPD | Remains iUPD unless iCPD confirmed based on further increase in: o previously identified T lesion iUPD SOM ≥ 5 mm and / or o NT lesion iUPD (prior assessment - need not be unequivocal PD) |

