| iUPD | iUPD | Yes | iUPD | Remains iUPD unless iCPD confirmed based on further increase in: o previously identified T lesion iUPD ≥ 5 mm and / or o previously identified NT lesion iUPD (need not be unequivocal) and /or o size or number of new lesions previously identified |
| Non-iUPD/PD | Non-iUPD/PD | Yes | iUPD | Remains iUPD unless iCPD confirmed based on o increase in size or number of new lesions previously identified |

* Using RECIST 1.1 principles. If no PSPD occurs, RECIST 1.1 and iRECIST categories for CR, PR and SD would be the same. ** in any lesion category. *** previously identified in assessment immediately prior to this TP.

All patients will have their iBOR from the start of study treatment until the end of treatment classified as outlined below.

Table S3:iRECIST Best Overall Response (iBOR)

| TPR1 | TPR2 | TPR3 | TPR4 | TPR5 | iBOR |
|------|---------------------------|--------------------|--------------------------|-------------------------------|------|
| iCR | iCR, iPR , iUPD, NE | iCR, iPR, iUPD, NE | iUPD | iCPD | iCR |
| iUPD | iPR, iSD, NE | iCR | iCR, iPR, iSD, iUPD, NE | iCR, iPR, iSD, iUPD, iCPD, NE | iCR |
| iUPD | iPR | iPR, iSD, iUPD, NE | iPR, iSD, iUPD, NE, iCPD | iPR, iSD, iUPD, NE, iCPD | iPR |
| iUPD | iSD, NE | PR | iPR, iSD, iUPD, NE | iPR, iSD, iUPD, iCPD, NE | iPR |
| iUPD | iSD | iSD, iUPD, NE | iSD, iUPD, iCPD, NE | iSD, iUPD, iCPD, NE | iSD |
| iUPD | iCPD | Anything | Anything | Anything | iCPD |
| iUPD | iUPD | iCPD | Anything | Anything | iCPD |
| iUPD | NE | NE | NE | NE | iUPD |

1. Table assumes a randomised study where confirmation of CR or PR is not required.
2. NE = not evaluable that cycle.
3. Designation "I" for BOR can be used to indicate prior iUPD to aid in data interpretation.
4. For patients with non-target disease only at baseline, only CR or non-CR/non-PD can be assigned at each TPR but is not shown in the table for ease of presentation.

5. Response and Stable Disease Duration (RECIST 1.1 and iRECIST)

Response duration will be measured from the time measurement criteria for CR/PR or iCR/iPR (whichever is first recorded) are first met until the first date that recurrent or progressive disease is objectively documented, taking as reference the smallest measurements recorded on study (including baseline).

Stable disease duration will be measured from the time of start of treatment until the criteria for progression are met, taking as reference the smallest sum on study (including baseline).

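### Appendix 5 section 3.1 and Table S2 disagree on whether first progression in another lesion type, most clearly a first new lesion, confirms iUPD; this touches only the exploratory 6-month iRECIST analysis

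*Protocol*

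**What the plan says.** Appendix 5, section 3.1, opens its rule with "iCPD is confirmed if further increase in tumour burden, compared to the last assessment, is seen as evidenced by one or more of the following". One listed condition is therefore enough. The second condition is that "RECIST 1.1 criteria are met in lesions types (target or non-target or new lesions) where progression was not previously identified", and it expressly includes further new lesions.

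Table S2, placed under section 3.2, assigns the response at each time point. Its prior-iUPD column is footnoted as applying to iUPD "in any lesion category", so it also covers a patient whose earlier iUPD was in a different lesion type. The relevant cells, written as target / non-target / new lesions, are:

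- iUPD unchanged or smaller / iUPD unchanged or smaller / Yes: "NLs confirms iCPD if NLs were previously identified and increase in size" (or in number).
- iUPD / iUPD / Yes: stays iUPD unless previously identified target or non-target iUPD increases further, or there is an increase in "size or number of new lesions previously identified".
- Non-iUPD / Non-iUPD / Yes: stays iUPD unless there is an "increase in size or number of new lesions previously identified".
- iUPD / iUPD / No: the non-target trigger is further increase in "NT lesion iUPD (prior assessment - need not be unequivocal PD").

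Protocol 8.3.6.1 and SAP 7.1 compare the arms on the proportion progression-free at 6 months by iRECIST, using the primary-endpoint method. Protocol 8.3.6.1 adds that "McNemar's Test will be used to estimate the concordance between the two outcome measures". Neither passage says whether iUPD or only iCPD counts as progression.

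**The concern.** The text and the table are two statements of one classification rule, and nothing says which prevails. Under Protocol 6.1.2.6 both the investigator and a blinded central radiologist score every scan by iRECIST. If one follows section 3.1 and the other Table S2, they can disagree on identical findings for no clinical reason.

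If iCPD is the 6-month event, a patient with a first new lesion who is held at iUPD by the table counts as progressed under RECIST 1.1 and progression-free under iRECIST. That looks like pseudoprogression, which is what the contrast between the two criteria is meant to detect, but here it would come from the table's wording.

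**Working it through.** **Reference figure.** The plan gives no figure on this point. As background, its 90% power (12 per arm, 1/12 versus 7/12 progression-free, one-sided 0.05) reproduces at 90.1% by enumerating the Pearson test. It concerns the primary endpoint and does not change.

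**Step 1: the same scans under both rules.**

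| Case | Earlier iUPD | Repeat scan | Section 3.1 | Table S2 |
|---|---|---|---|---|
| A | Target only | Target and non-target no longer progressing; first new lesion | iCPD | Stays iUPD (Non-iUPD / Non-iUPD / Yes) |
| B | Target only | Target still iUPD, growth under 5 mm; non-target not progressing; first new lesion | iCPD | No matching row |
| C | Target and non-target | Both unchanged; first new lesion | iCPD | Condition for iCPD not met (unchanged / unchanged / Yes) |
| D | Target only | Target still iUPD, growth under 5 mm; non-target iUPD for the first time; first new lesion | iCPD | Stays iUPD on a plain reading (iUPD / iUPD / Yes) |
| E | Target only | As D, no new lesion | iCPD | Stays iUPD on a plain reading (iUPD / iUPD / No) |

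Case A is the cleanest contradiction. In case C the cell keeps iUPD explicitly only when new lesions have not changed, so a first new lesion is left unconfirmed by default. Case B is a gap; the closest row, with unchanged iUPD and a new lesion, again asks for new lesions already on record.

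**Step 2: does anything else settle it?** The footnotes bring prior iUPD in any category under the column and tie previous identification to the immediately preceding assessment. Section 3.2 deals only with further progression of new lesions after an iUPD. None adds the missing route.

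**Step 3: can it matter by day 180?** Inputs: scans every 9 ± 1 weeks and a repeat scan 4–6 weeks after progression (Protocol 6.1.2.6); day 180 from C1/D1 (Protocol 8.3.4). Scan k falls at 63k ± 7 days, counted from C1/D1.

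- Scan 1: days 56–70; repeat at 56 + 28 = 84 to 70 + 42 = 112.
- Scan 2: days 119–133; repeat at 119 + 28 = 147 to 133 + 42 = 175.
- Scan 3: days 182–196, after day 180.

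Both repeat scans precede day 180. After iUPD at scan 1, scan 2 gives the table another chance to confirm. After iUPD at scan 2, no further scheduled scan falls before day 180. (Appendix 5 allows up to 8 weeks for the repeat scan, which would extend the second window to 133 + 56 = day 189.)

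**Step 4: size per patient, if only iCPD counts.** One patient is 1/12 = 8.3 points in an arm. For illustration, use the Pearson statistic z = [(y − x)/12] / √[p̄(1 − p̄)(2/12)], with x and y progression-free in the control and combination arms:

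- x = 1, y = 5: p̄ = 6/24, z = 0.333/0.177 = 1.886, one-sided p = 0.030 (exact unconditional 0.036).
- x = 1, y = 4: p̄ = 5/24, z = 0.250/0.166 = 1.508, one-sided p = 0.066 (exact unconditional 0.081).

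For the McNemar contrast, iCPD presupposes an iUPD that met RECIST 1.1 progression, so discordance from this source runs one way. The exact two-sided p for k such pairs is 2 × (1/2)^k: 0.25 (k = 3), 0.125 (4), 0.063 (5), 0.031 (6).

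**The case against.** The strongest reply is that the conflict is narrow and may often resolve itself.

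- **Scope.** A reader might infer that Table S2 contradicts section 3.1 wherever there was a prior iUPD. It does not. The iSD / iUPD / No and iUPD / Non-iUPD / No rows ask for further growth of non-target disease or of the target sum without requiring that lesion type to have progressed before, so they can be read consistently with the text. Text and table also agree on additional new lesions when some were already on record. This stands.
- **Ambiguity in case D.** Non-target lesions are noted at baseline. If previous identification refers to the lesion rather than to its iUPD, first non-target progression could confirm under the iUPD / iUPD / Yes row too. This weakens case D, but not case A.
- **Event definition.** If iUPD already counts as progression at 6 months, no patient's status differs between the two rules. This stands, and the documents leave it open.
- **Delay, not loss.** Once the first new lesion is on record, later growth or another lesion confirms iCPD under the table as well. This stands for iUPD at the first scan, provided imaging continues and disease grows. It helps less for iUPD at the second scan, since the next scheduled scan falls after day 180.
- **Weight.** A reader might infer that a few reclassified patients would decide the trial's result. The documents do not say how often confirmation would rest on a new lesion type alone, and they attach no decision to the McNemar test. The SAP's proposed efficacy table has no iRECIST line.
- **Stopping treatment.** A reader might link this to confirmed progression as a discontinuation reason in Protocol 4.8. Protocol 6.1.2.6 ties central review before discontinuation to RECIST 1.1 progression, so the documents support no more than a request to reconcile the passages.

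**Conclusion.** The contradiction is real for a first new lesion and, on a plain reading, for first non-target progression in the iUPD / iUPD / No row. The absent row is a separate gap. The consequence is limited to the exploratory 6-month iRECIST comparison and its McNemar contrast. It depends on two conditions: iCPD is the event, and no later scan confirms progression before day 180. Under those conditions each affected patient shifts an arm's rate by 8.3 points. The number affected cannot be estimated from the documents, and the p-values above only illustrate sensitivity at 12 per arm. The primary RECIST 1.1 endpoint, the sample size and the power are unaffected. Severity: minor.

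**What to change.** For deriving the iRECIST endpoint, give both readers one algorithm:

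1. In the prior-iUPD column of the four rows (unchanged iUPD / unchanged iUPD / Yes; iUPD / iUPD / Yes; Non-iUPD / Non-iUPD / Yes; iUPD / iUPD / No), add that iCPD is also assigned when RECIST 1.1 progression is newly met in a lesion type without iUPD at the prior assessment, including a first new lesion. The other rows need no change.
2. Add the missing row, target iUPD / non-target non-iUPD / new lesion Yes, with outcomes that follow section 3.1.
3. State in Protocol 8.3.6.1 and SAP 7.1 that iCPD is the iRECIST progression event at 6 months.

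Where confirmed progression in Protocol 4.8 may rely on the same appendix passages, those passages must be reconciled; no stopping rule is proposed here.

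The cost is the wording of one appendix table, one sentence in each analysis section and the derivation program. No new scans or patients are needed.

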3.2. New lesions

New lesions should be assessed and measured as they appear using RECIST 1.1 criteria (maximum of 5 lesions, no more than 2 per site, at least 10 mm in long axis (or 15 mm in short axis for nodal lesions), and recorded as New Lesions-Target (NLT) and New Lesion-Non-Target (NLNT) to allow clear differentiation from baseline target and non-target lesions.

New lesions may either meet the criteria of NLT or NLNT to drive iUPD (or iCPD). However, the measurements of target lesions should NOT be included in the sum of measures of original target lesions identified at baseline. Rather, these measurements will be collected on a separate table in the case record form.

PD is confirmed in the New Lesion category if the next imaging assessment, conducted at least 4 weeks (but not more than 8 weeks) after iUPD confirms further progression from iUPD with either an increase of at least 5 mm in the absolute value of the sum of NLT OR an increase (but not necessarily unequivocal increase) in the size of NLNT lesions OR the appearance of additional new lesions.

Table S2: Time-point (TP) iResponse

| Target Lesions* | Non-Target Lesions* | New Lesions* | Time Point Response | |
|--|--|--------------|---------------------|---|
| | | | No prior iUPD** | Prior iUPD**; *** |
| iCR | iCR | No | iCR | iCR |
| iCR | Non-iCR/Non-iUPD | No | iPR | iPR |
| iPR | Non-iCR/Non-iUPD | No | iPR | iPR |
| iSD | Non-iCR/Non-iUPD | No | iSD | iSD |
| iUPD with no change OR decrease from last TP | iUPD with no change OR decrease from last TP | Yes | NA | NLs confirms iCPD if NLs were previously identified and increase in size (≥ 5 mm in SOM for NLT or any increase for NLNT) or number. If no change in NLs (size or number) from last TP, remains iUPD |
| iSD | iUPD | No | iUPD | Remains iUPD unless iCPD confirmed based in further increase in size of NT disease (need not meet RECIST 1.1 criteria for unequivocal PD) |
| iUPD | Non-iCR/Non-iUPD | No | iUPD | Remains iUPD unless iCPD confirmed based on: o further increase in SOM of at least 5 mm, otherwise remains iUPD |
| iUPD | iUPD | No | iUPD | Remains iUPD unless iCPD confirmed based on further increase in: o previously identified T lesion iUPD SOM ≥ 5 mm and / or o NT lesion iUPD (prior assessment - need not be unequivocal PD) |
| iUPD | iUPD | Yes | iUPD | Remains iUPD unless iCPD confirmed based on further increase in: o previously identified T lesion iUPD ≥ 5 mm and / or o previously identified NT lesion iUPD (need not be unequivocal) and /or o size or number of new lesions previously identified |
| Non-iUPD/PD | Non-iUPD/PD | Yes | iUPD | Remains iUPD unless iCPD confirmed based on o increase in size or number of new lesions previously identified |

* Using RECIST 1.1 principles. If no PSPD occurs, RECIST 1.1 and iRECIST categories for CR, PR and SD would be the same. ** in any lesion category. *** previously identified in assessment immediately prior to this TP.

All patients will have their iBOR from the start of study treatment until the end of treatment classified as outlined below.

Table S3:iRECIST Best Overall Response (iBOR)

| TPR1 | TPR2 | TPR3 | TPR4 | TPR5 | iBOR |
|------|---------------------------|--------------------|--------------------------|-------------------------------|------|
| iCR | iCR, iPR , iUPD, NE | iCR, iPR, iUPD, NE | iUPD | iCPD | iCR |
| iUPD | iPR, iSD, NE | iCR | iCR, iPR, iSD, iUPD, NE | iCR, iPR, iSD, iUPD, iCPD, NE | iCR |
| iUPD | iPR | iPR, iSD, iUPD, NE | iPR, iSD, iUPD, NE, iCPD | iPR, iSD, iUPD, NE, iCPD | iPR |
| iUPD | iSD, NE | PR | iPR, iSD, iUPD, NE | iPR, iSD, iUPD, iCPD, NE | iPR |
| iUPD | iSD | iSD, iUPD, NE | iSD, iUPD, iCPD, NE | iSD, iUPD, iCPD, NE | iSD |
| iUPD | iCPD | Anything | Anything | Anything | iCPD |
| iUPD | iUPD | iCPD | Anything | Anything | iCPD |
| iUPD | NE | NE | NE | NE | iUPD |

1. Table assumes a randomised study where confirmation of CR or PR is not required.
2. NE = not evaluable that cycle.
3. Designation "I" for BOR can be used to indicate prior iUPD to aid in data interpretation.
4. For patients with non-target disease only at baseline, only CR or non-CR/non-PD can be assigned at each TPR but is not shown in the table for ease of presentation.

5. Response and Stable Disease Duration (RECIST 1.1 and iRECIST)

Response duration will be measured from the time measurement criteria for CR/PR or iCR/iPR (whichever is first recorded) are first met until the first date that recurrent or progressive disease is objectively documented, taking as reference the smallest measurements recorded on study (including baseline).

Stable disease duration will be measured from the time of start of treatment until the criteria for progression are met, taking as reference the smallest sum on study (including baseline).

6. Methods of Measurement

The same method of assessment and the same technique should be used to characterize each identified and reported lesion at baseline and during follow-up. Assessments should be identified on a calendar schedule and should not be affected by delays in therapy. While on study, all lesions recorded at baseline should have their actual measurements recorded at each subsequent evaluation, even when very small (e.g. 2 mm). If it is the opinion of the radiologist that the lesion has likely disappeared, the measurement should be recorded as 0 mm. If the lesion is believed to be present and is faintly seen but too small to measure, a default value of 5 mm should be assigned. For lesions which fragment/split add together the longest diameters of the fragmented portions; for lesions which coalesce, measure the maximal longest diameter for the "merged lesion".

6.1. Clinical Lesions. Clinical lesions will only be considered measurable when they are superficial and ≥ 10 mm as assessed using calipers (e.g. skin nodules). For the case of skin lesions, documentation by colour photography including a ruler to estimate the size of the lesion is recommended. If feasible, imaging is preferred.

- 6.2. Chest X-ray. Chest CT is preferred over chest X-ray, particularly when progression is an important endpoint, since CT is more sensitive than X-ray, particularly in identifying new lesions. However, lesions ≥ 20 mm on chest X-ray may be considered measurable if they are clearly defined and surrounded by aerated lung.
- 6.3. CT, MRI. CT is the best currently available and reproducible method to measure lesions selected for response assessment. This guideline has defined measurability of lesions on CT scan based on the assumption that CT slice thickness is 5 mm or less. When CT scans have slice thickness greater than 5 mm, the minimum size for a measurable lesion should be twice the slice thickness. MRI is also acceptable in certain situations (e.g. for body scans). Other specialized imaging or other techniques may also be appropriate for individual case.⁴ For example, while PET scans are not considered adequate to measure lesions, PET-CT scans may be used providing that the measures are obtained from the CT scan and the CT scan is of identical diagnostic quality to a diagnostic CT (with IV and oral contrast).
- 6.4. Ultrasound. Ultrasound is not useful in assessment of lesion size and should not be used as a method of measurement. If new lesions are identified by ultrasound in the course of the study, confirmation by CT is advised.
- 6.5. Endoscopy, Laparoscopy. The utilization of these techniques for objective tumour evaluation is not advised. However, they can be useful to confirm complete pathological response when biopsies are obtained or to determine relapse in trials where recurrence following complete response or surgical resection is an endpoint.
- 6.6. Tumour Markers. Tumour markers alone cannot be used to assess objective tumour response. If markers are initially above the upper normal limit, however, they must normalize for a patient to be considered in complete response.
- 6.7. Cytology, Histology. These techniques can be used to differentiate between PR and CR in rare cases if required by protocol (for example, residual lesions in tumour types such as germ cell tumours, where known residual benign tumours can remain). When effusions are known to be a potential adverse effect of treatment (e.g. with certain taxane compounds or angiogenesis inhibitors), the cytological confirmation of the neoplastic origin of any effusion that appears or worsens during treatment when the measurable tumour has met criteria for response or stable disease is advised to differentiate between response or stable disease and progressive disease.

